We will conduct a cluster RCT to determine the feasibility and acceptability of the MB-TXT intervention and calculate a preliminary effect size to determine a sample size for a future RCT. This RCT will also allow us to examine MB-TXT effects on proposed mechanisms underlying intervention efficacy. Cluster allocation by HV program minimizes contamination between study groups. We will work with 10-12 HV programs that have been trained on MB 1-on-1 and have working relationships with the PI. These programs provide a geographically, racially, and ethnically diverse set of recruitment sites. These programs are part of a network of Illinois HV programs overseen by the Illinois Governor's Office of Early Childhood Development which has supported scaling MB throughout Illinois and is enthusiastic about using text messaging to enhance intervention effectiveness. We will use a stepped wedge design—a form of RCT that involves sequential, but random, rollout of the intervention over multiple time periods. We have created two HV program clusters. Both clusters will initially implement MB 1-on-1 and will recruit MB participants for one quarter (i.e., three months) before crossing over to recruit MB-TXT participants for one quarter. MB-TXT's core curriculum is identical to MB 1-on-1 and adds a series of text messages throughout the curriculum.

Study Conditions:

MB 1-on-1. Half of our study participants (n=54) will receive MB 1-on-1. MB 1-on-1 is a manualized 12-session intervention divided into five modules. An introductory 2-session module establishes key

PROTOCOL TITLE: The Mothers and Babies Text Project

concepts related to stress, monitoring of one's mood, and ways in which one's mood influences one's internal thoughts and external environment; three 3-session modules correspond with key cognitive-behavioral elements: pleasant activities, thoughts, and social support/contact with others; a 1-session summary reviews content and identifies areas for future use of MB skills. Throughout MB, mood management skills are integrated using psycho-educational activities that encourage participants to understand connections between their mood and their activities, thoughts, and contacts with others. Content is tailored to specific needs and issues of pregnancy and the postpartum periods. Each MB session lasts 15-20 minutes and is delivered as part of a regularly scheduled home visit.

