Analysis for Aim 2 is limited to the fact that this is a pilot study. As such, we will compare MB and MB-TXT groups at the individual level (not adjusting for potential clustering effect of either home visitor or HV program). The data will also provide key insights for future studies on how correlated the BDI scores will be over time, as longitudinal data during this postpartum period is not readily available. To address hypothesis 2, the first step in mediation is to determine the mediator's association with the criterion (group), as well as the outcome. The sample provides 80% power to detect effect sizes of 0.59 using two sided Mann Whitney tests at a type I error rate of 5% (for the between group comparison of potential mediators: negative cognitions, behavioral activation, use of support systems, mood regulation), as well as 80% power to detect correlations as small as 0.287 (comparing BDI to

PROTOCOL TITLE: The Mothers and Babies Text Project

the potential mediators). Pilot data will allow us to examine potential ranges of Intraclass Correlation Coefficients (ICC), which we need to account for in a larger RCT. These data will allow us to explore whether randomization should be done at HV program level, or the home visitor level. This sample provides 80% power to detect ICCs of 0.179 (13-14 observations at 10-12 HV programs), or of 0.261 (3 observations in 36 home visitors).

Phase 2 (FAB Development and Pilot)

Study Activities Include:

- Focus Groups with HV Clients (n=16) and their male partners (n=16)
- Development of FAB
- Pilot FAB
- Note: The research team submitted a modification to add/update details about the focus groups for phase 2 of the study. Focus group guide for these groups was submitted a modification for versions 7 of the protocol.
- Note: The research team submitted a modification to add/update details for the FAB intervention pilot in phase 2 of the study including recruitment materials. Modifications are included in version 8 of the protocol.
- FAB Post Intervention Focus Groups and Key Informant Interviews
- Note: The research team will submit a modification to add/update details about the FAB post intervention focus groups and key informant interviews. The modification will include focus and key informant consents, the focus group guide and the key informant interview guide.
-

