6.0 Incomplete Disclosure or Deception: N/A

7.0 Recruitment:

Study Participants: During phase 1, we will recruit 108 study participants from each of the participating HV programs. We will enroll 108 HV clients at 10-12 HV programs, 54 women will receive Mothers and Babies 1-on-1 without text message enhancements and 54 women will receive Mothers and Babies 1-on-1 with text message enhancements. Of the 108 women, 16 will be recruited for focus groups phase 2 of the study.

During phase 2 of the study we will conduct focus groups with the identified 16 women from the 108 group that participated in phase 1 of the study. We will also include their male partners (n=16) in two focus groups of 8 participants. Additionally we will recruit 36 women and their male partners to participate in the FAB Pilot Study.

Home Visitors: We will recruit approximately 36 home visitors from 10-12 participating HV programs throughout the state of Illinois. All HV programs recruit women at high risk for poor pregnancy and/or parenting outcomes via referrals from prenatal care clinics, community outreach, and current program participation. All of the home-visitors who are being recruited through the participating home-visiting sites have been previous trained and are currently implementing Mothers and Babies 1-on-1. Home visitors that have not been trained will receive an in-person training (see training section for more detail). Each home-visitor will identify 1-4 client that will participate in study activities, of these clients 1-2 will receive MB without Text and 1-2 will receive MB with Text. All home-visitors will implement MB without text and MB with text. Programs will initially implement MB 1-on-1 and will recruit MB participants for six months before crossing over to recruit MB-TXT participants for 6 months. To pilot FAB 1-3 home-visitors from each program will identify 1-4 client dyads that will participate in FAB pilot study activities; Home-visitors who will implement FAB will recruit dyads.

We anticipate 16 home-visitors will participate in focus groups during phase 1 and 2 of the study. 10-12 HV programs will be recruited to implement the FAB pilot.

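### Phase 1 asserts a randomly staggered stepped wedge without specifying it, and the planned Aim 2 comparison ignores calendar time

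*Combined protocol and SAP*

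**What the plan says.** Section 4.0, Program Implementation (MB-TXT RCT), describes a cluster RCT and defines the stepped wedge as "a form of RCT that involves sequential, but random, rollout of the intervention over multiple time periods". It gives the home visiting program as the unit: "Cluster allocation by HV program minimizes contamination between study groups". It continues: "We have created two HV program clusters", and then: "Both clusters will initially implement MB 1-on-1 and will recruit MB participants for one quarter (i.e., three months) before crossing over". The MB-TXT window that follows has the same length.

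Section 7.0, Home Visitors, keeps the same order but a different window: programs "will recruit MB participants for six months before crossing over to recruit MB-TXT participants for 6 months". It adds: "All home-visitors will implement MB without text and MB with text".

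For Aim 2, section 4.0 says "Analysis for Aim 2 is limited to the fact that this is a pilot study" and that "we will compare MB and MB-TXT groups at the individual level", without adjusting for home visitor or program. Section 14.0 repeats this and gives power for t-tests on the BDI: 46 per arm and effect sizes of 0.59 (two-sided) or 0.52 (one-sided). The mediators are to be compared by Mann-Whitney tests. Section 1.0 says the effect size from Aim 2 could be used, with other data, to size a later trial.

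**The concern.** A stepped wedge separates the intervention from time in two ways: clusters cross over at different, randomly ordered times, and the analysis allows for period. Here the first is asserted but not specified. The text available does not say whether chance decided cluster membership, order or start date, and it gives no start or crossover date for either cluster. The second is absent. As written, the plan cannot be told apart from a design in which all programs cross together, where MB-TXT and the later period are the same thing.

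The documents themselves suggest why outcomes might move with time. The same home visitors deliver both conditions, MB first. Some programs are new to MB, and supervision begins after first implementation (section 4.0, Training and Supervision). Growing experience, season or staff change could each shift outcomes between windows.

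The preliminary effect size is at stake. It is an input to the next trial's sample size, and it would carry any such shift without warning. The only consequence of pilot status that the plan names is the lack of adjustment for clustering.

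**Working it through.** **Inputs from the documents.** 108 women, 54 per condition; 15% attrition, so 54 × 0.85 = 45.9, or 46 per arm (92 in all); 10-12 programs; two clusters; 5% type I error. **Assumptions, because the documents give no figures:** the size of the drift, the cluster calendar, the ICC, the baseline-follow-up correlation r, and even recruitment within windows.

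**1. The plan's own figure.** With 46 per arm and a two-sided 5% t-test, the noncentral t distribution gives 79.9% power at 0.59 SD. The effect detectable with 80% power is 0.590 two-sided and 0.522 one-sided. The stated figures reproduce.

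**2. Enrolment lag.** Suppose a program starts at time s with windows of length w. The mean enrolment time is s + w/2 for MB and s + 3w/2 for MB-TXT. The difference is w whatever s is, so staggering the clusters does not remove it from an unadjusted comparison.

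**3. How much of a time change enters the effect.**

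| Schedule (assumed) | Linear drift | One-off step |
|---|---|---|
| Simultaneous crossover, step at the crossover | 100% | 100% |
| Clusters one window apart, step between periods 1 and 2 or 2 and 3 | 100% | 50% |
| Six-month windows, clusters three months apart, step between quarters | 100% | 25-75% |

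In the second row, for example, MB is recruited in periods 1 and 2 and MB-TXT in periods 2 and 3. A step after period 1 affects all MB-TXT women and half the MB women, so 1 − 0.5 = 50% passes through.

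**4. Illustrative false-positive rate.** With no true effect and drift δ SD per window, the noncentrality is δ × √(46/2). Under simultaneous crossover, δ = 0.1 / 0.2 / 0.3 gives 7.6 / 15.8 / 29.6%.

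If change in BDI is analysed, a shift common to baseline and follow-up cancels. A shift of 0.2 SD at follow-up only is divided by √(2 − 2r) and gives 12.6 / 15.8 / 23.2% at r = 0.3 / 0.5 / 0.7.

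**5. What period adjustment would cost.** The unadjusted SE is √(2/46) = 0.209. Detectable effect is taken as 2.80 × SE (normal approximation).

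- *Simultaneous crossover.* Treatment and categorical period cannot be separated (rank 2 of 3). With a linear trend on enrolment date, the variance is 4.0 times as large: SE 0.417, detectable effect 1.17 SD.
- *One-window stagger, ICC 0.* Only the shared period informs the effect, about 23 against 23: SE = √(2/23) = 0.295, detectable effect 0.83 SD. With a random program effect and ICC 0.02 to 0.179, it is 0.85 to 1.06 SD. The upper ICC is the value section 4.0 says the sample could detect, used here only as an upper illustration.
- *Six-month windows, three-month stagger.* Only one quarter has the clusters in different conditions. At ICC 0, 92/8 = 11.5 women per cell gives SE = √(2/11.5) = 0.417 and 1.17 SD. Over the same ICC range it is 1.17 to 1.20 SD.
- *Two-window stagger.* The clusters never overlap under different conditions, and the effect is not estimable.

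**6. Bias against variance (ICC 0, linear drift).** Root mean square error of the unadjusted estimate is √(0.209² + δ²) = 0.23 / 0.29 / 0.37 at δ = 0.1 / 0.2 / 0.3. Period adjustment gives lower total error only if δ exceeds √(0.295² − 0.209²) = 0.21 with the one-window stagger, or √(0.417² − 0.209²) = 0.36 with the six-month schedule.

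**The case against.** The strongest reply is that every stepped wedge begins with all clusters in control, so the MB-first order fits the label, and section 4.0 does say the rollout is random and sequential. That stands. A reader might infer from the common order that nothing was randomised, or that Phase 1 is certainly a before-after study. The documents support neither inference; they leave the matter open.

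A reader might also infer that any change between windows is credited in full to the text messages. That is true only for simultaneous crossover or linear drift. A one-off step passes in part under a stagger, a common shift cancels in a change score (H1 speaks of reductions), and drift could equally hide a benefit.

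Nor is the power statement wrong: 0.59 SD is correct for the test it describes.

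Finally, making a period-adjusted model the sole analysis could worsen a pilot estimate, as step 6 shows. That also stands, and it is why the adjusted estimate is asked for beside the unadjusted one. What the reply does not answer is the missing calendar and random element, the conflict on window length, and the absence of any warning about time.

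**Conclusion.** The concern holds in this form: the random staggered crossover is asserted without being specified, and the planned comparison is confounded with calendar time on any schedule the text allows. If the analysed outcome drifts, the Aim 2 effect size is biased, by the full drift per window in the worst case and in either direction. At assumed drifts of 0.1 to 0.3 SD per window, the nominal 5% error rate becomes about 8 to 30% under simultaneous crossover.

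These sizes rest on assumed drift and even recruitment; the documents neither show that drift exists nor give its size. The detectable effects of 0.83 SD or more depend on the schedule, so none is offered as a replacement for 0.59 SD. The text-message feasibility and acceptability measures of Aim 1 are not affected. Part of section 17.0 (staff qualifications) was not available; it is unlikely to hold the allocation method, but that could not be checked.

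**What to change.** 1. Reconcile sections 4.0 and 7.0 on window length. State what was drawn at random and each cluster's start and crossover dates.
2. If crossover was randomly staggered and the clusters overlap in calendar time under different conditions, report a period-adjusted estimate (fixed periods, program as a random effect) alongside the unadjusted one. Give its detectable effect for the actual schedule, and say that 0.59 SD applies only to the unadjusted test.
3. If crossover was simultaneous, not random, or without such overlap, drop the RCT and stepped-wedge labels for Aim 2 and report a non-randomised before-after comparison. Any trend model is then a sensitivity analysis with its assumption stated.
4. In all cases, say whether 6-month BDI or its change from baseline is analysed, and state the confounding with time wherever the effect size is used to plan the next trial.

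The cost is wording, a little analysis work and a wider interval for the adjusted estimate. No extra women and no change to recruitment are needed. Redesigning the allocation is not proposed, since section 4.0 (Participant Outreach and Contact) indicates that participants are already enrolled.

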During phase 2 of the study we will conduct focus groups with the identified 16 women from phase 1 of the study. We will also include their male partners (n=16) in two focus groups of 8 participants. All focus groups will only be held in English. Additionally we will recruit 36 women and their male partners (36 dyads from 10-12 HV programs) to participate in an uncontrolled pilot of the FAB intervention at two HV programs not participating in the Phase 1 RCT. We will conduct additional, qualitative data from 22 male partners after receiving FAB. Our informed consent from includes an option to be contacted for future research studies, we will only contact participants who indicate “yes” to this option for qualitative data collection activities (focus groups and key informant Interviews) after completing FAB.

Study Participants

Phase 1 (MB-TXT RCT)

We will recruit 108 study participants from 10-12 Home Visiting programs. English or Spanish-speaking women ≥ 16 years old enrolled in HV programs who are in their 1st or 2nd trimester (≤ 26 weeks) will be eligible for enrollment; across the 10-12 HV programs ~80% of women meet these criteria.

Phase 2 (FAB Development and Pilot)

(A) Focus Groups for FAB Development

We will recruit a total of 48 focus group participants, consisting of 16 female clients who participated in MB-TXT in Phase 1, 16 male partners of the female focus group participants, and 16 Home Visiting supervisors/managers and home visitors from the HV programs. The focus groups with the Home Visiting supervisors/managers and home visitors will be conducted during Phase 1 and 2 of the study. The focus groups will consist of 16 Home Visiting supervisors/managers and home visitors from the HV programs. The focus groups in phase 2 will consist of 16 female clients who participated in MB-TXT in Phase 1 and 16 male partners of the female focus group participants. All focus groups will only be held in English.

(B) FAB Pilot Study

We will recruit 36 women and their male partners (36 dyads from 8-10 HV programs). Eligible women (n=36) may be English speaking, ≥ 18 years old and enrolled in HV programs who are pregnant or

PROTOCOL TITLE: The Mothers and Babies Text Project

have a young child or children. Eligible men (n=36) may be English speaking, ≥ 18 years old, partners of female participants. We will recruit a total of 22 male partners who have received FAB (post-intervention) for focus group and key informant interviews.

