Home Visiting Programs

The 10-12 HV programs that use either the Healthy Families America (HFA) or Parents as Teachers (PAT) model. HFA and PAT are evidence-based⁷¹ paraprofessional HV models that enroll women prenatally and continue services until a child's second birthday (HFA) or entry into kindergarten (PAT). Both HFA and PAT recruit women at high risk for poor pregnancy and/or parenting outcomes via referrals from prenatal care clinics, community outreach, and current program participants. Both the HFA and PAT models call for weekly or bi-weekly home visits during pregnancy and the first six months postpartum. English or Spanish-speaking women ≥ 16 years old enrolled in HV programs who are pregnant will be eligible for enrollment in Phase 1 of the study. English speaking dyads; women ≥ 18 years old enrolled in HV programs and their male partners ≥ 18 years will be eligible for enrollment in Phase 2 of the study. Across the HV programs ~80% of women meet these criteria.

Vulnerable Populations

We will enroll pregnant women in both studies given that the Mothers and Babies Course can be delivered prenatally as a postpartum depression prevention intervention. In Phase 1, we will offer participation to pregnant women, ages 16 and older, knowing that the client population of HV programs is younger, on average, than the general population. In Phase 2, we will offer participation to pregnant women or have a young child or children who are enrolled in HV, ages 18 and older. Mothers and Babies has been used in similar HV settings in the state of Illinois and nationally, with high ratings of acceptability and usefulness and no ill effects of participation detected.

4.0 Procedures Involved:

Phase 1 (MB-TXT RCT)

Study Activities Include:

- Recruitment of participants for MB / MB + Text RCT
- Focus Groups with Home Visiting supervisors/managers and home visitors (2 Groups of 8, n=16)

Program Implementation (MB-TXT RCT)

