
Phase 1 Focus Groups

We will also recruit and conduct two focus groups with 16 HV supervisors/managers and home visitors beginning in phase one and into phase 2 of the study.

Training and Supervision of HV programs. The majority of participating All HV programs have been trained on MB 1-on-1 and are currently implementing the curriculum. Programs new to the MB Course will receive in-person training from the PI and/or study team. All programs will receive a half-day refresher training on MB along with guidelines on implementing MB-TXT conducted by Co-I [name] and PI [name]. All programs will receive supervision from PI [name] after the first implementation of the intervention begins at the HV programs

Participant Screening: Participants will initially be screened for eligibility criteria by their home visiting program sites. Upon permission from the potential study participant, program sites will fill out a referral form, which will include the potential study participants name and contact information, and send it to the research team. The HV will explain the study and provide a brochure with study details during the referral process. Once the program sites refer potential study participants, a member of the study team will call the participant using the "Phone Script for Referrals" to screen the potential study

participant for eligibility criteria and move forward with the consent process either via telephone or a REDCap survey link.

Participant Outcomes Surveys:

Clients MB TEXT: Participant outcomes will be collected at three time points—baseline and 6 months post-intervention. Participants will receive \$20 remuneration at the baseline and 6-months, assessments. \$20 remuneration will be in the form of a Northwestern PNC stored-value card (Visa Gift-Card).

Home Visitors: Home visitors will be asked to respond to a REDCap survey items after completing each MB session to assess if clients came to the session having completed their personal project, implemented session, and next scheduled session date. Home visitors will measure clients' perceived utility and comprehension of text messages by asking clients to rate the extent to which each of the 3 text messages received between sessions was a) useful and b) easy to understand. Questions will be on a 4-point Likert Scale and will be asked of clients at the end of each MB session. These data will be inputted into the HealthySMS system.

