Focus Groups: There will be six focus groups during the study. Two focus groups with HV supervisors, managers, and home visitors will take place during phase 1 and 2. Four focus groups with clients and their partners will take phase during phase 2. All focus group participants will receive \$30 remuneration in the form of a Northwestern PNC stored-value card (Visa Gift-Card).

Related to Aim 1, MB-TXT feasibility and acceptability data will be collected from clients and home visitors. Similar to previous SMS studies, we will use percentage of text responses as an indicator of "read" messages. We will assess home visitor adherence to the MB-TXT protocol by using archived data from HealthySMS to calculate percentage of texts sent at appropriate intervals, as stated in the MB Instructor Manual. Home visitors will complete a brief web-based REDCap survey after completing each MB session to assess if clients came to the session having completed their personal project. Using a 4-point Likert Scale, home visitors will also ask clients to rate the extent to which each of the 3 intersession texts was a) useful and b) easy to understand; these data will be entered into REDCap. Related to Aim 2, participant outcomes will be collected via survey at baseline and 6 months. Data will be collected and managed using REDCap electronic data capture tools hosted at Northwestern. Participants will receive \$20 remuneration for each assessment. At each assessment, a link to REDCap will be sent to study participants who can complete the assessment on any web platform (smartphone, tablet, and computer). The Project Manager or Research Assistant will complete assessments by phone for participants who prefer not to use REDCap. Depressive symptoms, as measured by the the Beck Depression Inventory-II (BDI)¹⁰⁰ a 21-item self-report measure is our primary outcome. Secondary outcomes, which map onto the hypothesized mechanisms for influence on depressive symptoms are: cognitive structuring (Experiences Questionnaire),⁸⁵ behavioral activation (Behavioral Activation Depression Scale),⁸⁶⁻⁸⁸ social support (MOS Social Support Survey),⁸⁹ and mood regulation (Negative Mood Regulation Scale).^{90,91} We estimate 15% attrition at 6months, resulting in 46 participants per arm; previous MB trials conducted by PI [name] had 12 month attrition rates <10% and we will use similar procedures for minimizing attrition.

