
Relationship with partner will be measured using the Revised Dyadic Adjustment Scale (RDAS) cohesion subscale. The RDAS cohesion subscale is most relevant to this study and measures items such as engaging in activities together. The cohesion subscale consists of 4 items, each of which asks respondents to rate certain aspects of his/her relationship on a 5- or 6- point scale. Higher scores indicate greater relationship satisfaction. The RDAS has demonstrated excellent internal consistency.⁹⁷

Fathers' involvement with child will be measured using the 10-item Father Engagement Scale (Dyer et al., 2015) which measures the number of times per month fathers engage in different types of activities with their child.

Perceived social support from partner will be measured using the Social Support Effectiveness-Questionnaire (SSE-Q) a 25-item version (Rini et al., 2011, J Consult Clin Psychol).

Participant Outreach and Contact: Study participants will be contacted at the following time points throughout the study:

1. Upon referral into the study. This contact will be from a member of the research team in order to conduct eligibility screening and review the study and next steps for consent and assessments
2. To schedule and/or conduct assessments by phone or REDCap survey link at baseline, post intervention, 3 and 6 months.
3. Text Messages after each session (MB +Text Only and FAB)
4. To check in with the study participants to make sure the study team has up to date contact information for the participant, as well as to stay engaged and build a rapport with the participant.
5. If the study participant is selected to participate in a focus group, research staff will call and coordinate focus group logistics.
6. Congratulation cards will be sent to each study participant after the birth of their baby
7. An information sheet will be mailed to notify participants who were previously consented and currently enrolled about the study being included in ClinicalTrials.gov and the change to the follow-up time points. We will only be following up at 6 months post-intervention and not at 9 month post-intervention.

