The Co-PI ([name]), Research Project Manager will conduct the focus groups. All focus group participants will be asked to provide informed consent prior to participating in the focus groups. Consent forms will clearly indicate that some study participants will be asked to participate in this additional data collection activity.

For Phase 1, we will enroll only pregnant women, given that our Mothers and Babies Course is delivered prenatally as a postpartum depression prevention intervention. We will offer participation to pregnant women, ages 16 and older. Each HV program will send contact information for an eligible participant to the Program Manager. The Manager or Research Assistant will contact these women to introduce women to the study, answer questions about participation, and ascertain interest in study participation. For women expressing interest, the Manager or Research Assistant will send an link to the REDCap data collection portal via email or text message, or Facebook message to conduct the baseline assessment. Participants that do not have access to online resources will be consented verbally and the baseline assessment will be conducted over the phone. Second, we will enroll HV supervisors/managers to participate in two focus groups. Consent will also be conducted in person by the Program Manager on the day the focus groups take place (prior to the focus groups).

For Phase 2, we will enroll two sets of study participants. First, we will enroll HV clients and their male partners of women participating in MB-TXT during Phase 1 to participate in four focus groups. Two focus groups will consist of 8-6 HV clients. Two separate focus groups will consist of 6-8 of their male partners. The Program Manager will administer the focus group consent in person on the day the focus groups take place (prior to the focus groups). We will enroll who are pregnant or have a young child or children and their male partners enrolled in HV and their male partners 18 years and older for our uncontrolled pilot of the FAB intervention. We will use processes similar to the ones described above to consent these individuals via REDCap prior to their baseline assessments. Again, for those individuals who choose not to consent via REDCap, phone consent will be conducted by the Program Manager or Research Assistant.

9.0 Process to Document Consent:

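### On the current procedures Phase 1 gives no woman two postpartum BDI scores, so it cannot supply the longitudinal postpartum data cited; separately, the 6-month time origin and the entry window are each stated two ways

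*Combined protocol and SAP*

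**What the plan says.** All references are to the combined protocol and SAP.

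- **The claim.** Section 4.0, Phase 1, Aim 2 analysis: the pilot will inform future studies on "how correlated the BDI scores will be over time, as longitudinal data during this postpartum period is not readily available".
- **Baseline.** Section 8.0: "For Phase 1, we will enroll only pregnant women". The baseline BDI is therefore prenatal.
- **Follow-up.** Section 4.0, Participant Outcomes Surveys, clients: "Participant outcomes will be collected at three time points—baseline and 6 months post-intervention" (three points announced, two named). Section 4.0, Aim 2 outcomes: "participant outcomes will be collected via survey at baseline and 6 months", with no origin for the 6 months. Section 4.0, Participant Outreach and Contact, item 7: "We will only be following up at 6 months post-intervention and not at 9 month post-intervention".
- **Entry.** Section 3.0, Study Participants, Phase 1, admits women "who are in their 1st or 2nd trimester (≤ 26 weeks) will be eligible for enrollment". Section 3.0, Home Visiting Programs, admits women aged 16 or over "enrolled in HV programs who are pregnant will be eligible for enrollment in Phase 1 of the study". Section 8.0 also sets the age limit without a gestational one.
- **Other visit schedules still in the text.** Table 1 (Phase 1) lists follow-up demographics at 3 and 6 months. Item 2 of the contact list gives baseline, post-intervention, 3 and 6 months, not split by phase. Section 12.0 pays for three surveys but names two. Section 14.0 gives baseline, 6 and 9 months.

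No assessment is timed from delivery.

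**The concern.** A correlation between repeated postpartum scores needs at least two postpartum scores per woman. A prenatal baseline with one follow-up cannot give that, whatever the sample size. Someone planning the next RCT with repeated postpartum BDIs could take a prenatal-to-follow-up correlation from this pilot and use it as if it were a correlation between postpartum visits.

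The other two points concern when the single follow-up BDI falls. It is the primary outcome and the source of the Aim 2 effect size. If its time origin is unclear, sites may assess women at different stages. If the entry rule is unclear, screeners cannot tell whether a woman at, say, 34 weeks is eligible. In addition, programs recruit MB first and MB-TXT afterwards (sections 4.0 and 7.0), so the arms fill in different calendar periods and nothing in the plan balances gestational age between them.

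**Working it through.** **1. Number of pairs.** The plan's figure reproduces: 54 × (1 − 0.15) = 45.9, so 46 per arm and 2 × 46 = 92 women with a follow-up BDI.

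**2. Postpartum scores per woman, current procedures.** Baseline contributes 0 (all women are pregnant) and the single follow-up contributes at most 1. Women with two or more: 0 of 92. The count is the same under either entry window and either time origin.

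**3. What can be estimated.** The correlation r between prenatal baseline and follow-up, from about 92 pairs. The documents give no expected r, so a range is shown. The 95% interval by Fisher's z is tanh(atanh r ± 1.96/√(92 − 3)):

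- r = 0.3: 0.10 to 0.48
- r = 0.5: 0.33 to 0.64
- r = 0.7: 0.58 to 0.79

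**4. When the follow-up falls.** Assumptions: delivery at 40 weeks; 6 months = 26 weeks; the course starts at entry. Twelve sessions (section 4.0) at weekly or bi-weekly visits (section 3.0) span 11 × 1 = 11 to 11 × 2 = 22 weeks from first to last.

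Weeks postpartum = entry week + lag − 40, with lag 26 from baseline, or 11 + 26 = 37 to 22 + 26 = 48 from course end.

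| Entry week | Clock from baseline | Clock from course end |
|---|---|---|
| 6 | −8 (still pregnant) | 3 to 14 |
| 14 | 0 | 11 to 22 |
| 26 | 12 | 23 to 34 |
| 39 (only if there is no cap) | 25 | 36 to 47 |

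The two clocks differ by the course length, 11 to 22 weeks. From baseline, a woman is still pregnant at follow-up if she enters before week 40 − 26 = 14. From course end with weekly sessions, that requires entry before week 40 − 37 = 3; with bi-weekly sessions it cannot occur.

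**5. How many could be affected on the baseline clock.** The documents give no distribution of entry week. If it were uniform from week a to week 26, the share still pregnant is (14 − a)/(26 − a): 8/20 = 40% for a = 6, 6/18 = 33% for a = 8, and 2/14 = 14% for a = 12 (about 37, 31 and 13 of 92). With no cap (to week 40) the shares are 8/34 = 24%, 6/32 = 19% and 2/28 = 7%.

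**6. Leftover schedules.** Some would give two postpartum scores. At 6 and 9 months from baseline, women entering at week 14 or later would have both. At 3 and 6 months post-intervention (3 months = 13 weeks), so would women entering from week 40 − (11 + 13) = 16 with weekly sessions, or 40 − (22 + 13) = 5 with bi-weekly sessions. The zero in step 2 therefore depends on the single 6-month follow-up being the schedule in force.

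**The case against.** **The sentence mainly promises a correlation of BDI over time; the postpartum phrase only gives the reason.** This stands in part. A reader might infer that no BDI correlation over time can be estimated. The documents do not support that: the prenatal-to-follow-up correlation is estimable, and it is useful for a future trial with a prenatal baseline. No power figure in the plan depends on a postpartum-to-postpartum correlation. The reason given still describes data that Phase 1 will not hold. Phase 2 does measure BDI at baseline, 3 and 6 months in women who may already have a child, but it is an uncontrolled pilot of 36 women and the sentence does not rely on it.

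**The visit schedule is not settled.** Correct, and the count of zero is conditional. Item 7 of the contact list, which withdraws the 9-month visit, makes one 6-month follow-up the best reading. The other passages still need to agree with it.

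**Where an origin is stated for Phase 1, it is post-intervention.** Correct. A reader might infer that some women will be assessed before birth; that follows, in practice, only if the unanchored 6 months is counted from baseline. That reading is not idle, because the text-message stipend in section 4.0 is limited by months from baseline.

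**The wider entry wording may be shorthand.** Plausible: both section 3.0 passages give about 80% of women as eligible. But both are worded as eligibility rules for the same phase, and only one has a gestational limit.

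**Timing from the intervention is legitimate.** Agreed. H1 concerns depressive symptoms, and the plan need not anchor to birth. Delaying visits until after delivery would make the interval from intervention to assessment uneven, so it is not proposed here.

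**Imbalance in gestation is conjecture.** Agreed that it is only a risk; the same programs and home visitors recruit both arms. Sequential recruitment is reason enough to report it.

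**Conclusion.** The point holds in three separate parts.

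- On the current procedures 0 of about 92 women have two postpartum BDI scores, so Phase 1 cannot fill the gap that the Aim 2 analysis cites. What it can give is one prenatal-to-follow-up correlation, blurred by varying time since birth.
- The primary outcome's time origin is stated in two places and missing in a third. The two readings differ by about 11 to 22 weeks.
- Phase 1 entry is stated with and without a 26-week limit.

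A reader might infer that the first part results from the other two, and that tying the visit to birth or settling the entry window would restore the missing pair. It would not: the cause is a prenatal baseline with a single follow-up. Origin and window affect only when that follow-up falls and how widely its timing spreads. Nor do the documents show that the arms differ in gestational age.

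The timing figures rest on a 40-week term, 26 weeks for 6 months, and sessions delivered without gaps from entry. The shares still pregnant also rest on assumed uniform entry.

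**What to change.** 1. In the Aim 2 analysis (section 4.0), replace the claim with: the correlation between the prenatal baseline BDI and the single follow-up BDI.
2. State one time origin for the 6-month BDI throughout. Bring into line with it the three time points in Participant Outcomes Surveys, Table 1, item 2 of the contact list (split by phase), the survey count in section 12.0, and the schedule in section 14.0.
3. Make the Phase 1 entry criterion the same in both parts of section 3.0 and in section 8.0. The choice of limit is the sponsor's.
4. Report gestational age at entry and weeks since delivery at follow-up, by arm. Add a sensitivity analysis of the BDI comparison adjusted for gestational age at entry. That covariate is fixed before the course begins, whereas weeks since delivery at follow-up can also depend on how long the course takes.

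Cost: wording changes, one sensitivity analysis, and a delivery-date field if none exists. The follow-up form items are not shown, and the cards sent after birth suggest that births are already tracked. No extra visit or participant is needed.
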